All subjects will undergo a fat tolerance test on two different days, in random order, with two different amounts of lipid in the meal, as described above in preliminary data. From the blood samples, we will measure the level of LPS and LBP in plasma, as well as the LPS and LBP in each lipoprotein fraction to determine whether more dietary lipid leads to a higher level of LPS in plasma. We will also determine whether LPS-lipoprotein levels change in a dynamic fashion following the meal. For example, if LPS remains associated with TG-rich lipoproteins, then the LPS will likely be cleared through lipolysis in adipose, and then the remaining remnant-LPS cleared by the liver, and liver insulin resistance may be an important effect of lipoprotein-LPS. However, if LPS is transferred to HDL, this could be due to the LBP content of HDL, and could represent another important function for HDL (i.e. clearance of LPS).

Subjects will then begin taking rifaximin 550 mg BID or placebo for 8 weeks. Rifaximin is poorly absorbed from the gut, has been shown to decrease plasma LPS in several studies (2;3;28), and is used acutely for traveler's diarrhea, and chronically for treatment of diverticulitis, hepatic encephalopathy, bacterial overgrowth, and irritable bowel syndrome (66;67). In clinical trials, the side effects of rifaximin are generally indistinguishable from placebo, and there is no evidence for weight loss or nutrient malabsorption (68) (see human subjects). After 8 weeks of rifaximin, all subjects will repeat the lipid tolerance tests (low- and high fat).

To verify the change in gut microbiota, the major classes of gut bacteria will be assayed from a stool sample before and after rifaximin treatment using nexgen targeted sequencing of 16S RNA, as described (69).

Specific Aim 2. We will determine whether a change in the gut microbiota from rifaximin treatment will decrease adipose inflammation and improve insulin resistance. In this aim we will determine whether the changes in gut microbiota and plasma LPS induced by rifaximin will affect adipose tissue inflammation and insulin sensitivity. After treatment with the antibiotic rifaximin for 8 weeks, the insulin sensitivity testing and adipose biopsies will be repeated to determine whether the antibiotic treatment changes inflammation and insulin sensitivity.

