This study involves fat biopsies from subjects under local anesthesia. Because it is difficult to obtain enough adipose tissue from a needle biopsy, incisional fat biopsies will be necessary. [name] has performed hundreds of such biopsies on outpatients undergoing studies on the effects of feeding, obesity, and diabetes, and insulin sensitizer drugs, and the complication rate has been very low, and patient acceptance of these procedures has been excellent. The biopsies will be performed under local anesthesia by the principal investigator or his designate (eg, a well-trained physician assistant). No patient will have a biopsy if it appears to represent an unacceptable risk, such as platelets <75,000, evidence of moderate platelet dysfunction, chronic aspirin use, or hematocrit < 30. In addition, we will measure body composition by DEXA.

We will recruit subjects without regard to ethnicity, and will study no vulnerable populations.

Intervention. After the above procedures, subjects will then begin taking rifaximin in a dose of 550 mg BID. This antibiotic is poorly absorbed from the gut, and is used routinely for traveler's diarrhea, and for prolonged periods for treatment of diverticulitis, hepatic encephalopathy, bacterial overgrowth, and irritable bowel syndrome (66;67). After 8 weeks of treatment with rifaximin, all subjects will repeat all the procedures above, including clamp, OGTT, lipid tolerance tests (low fat and high fat) and fat biopsies.

Compliance. It will be critical to retain patients in this program, and we will only select patients that are highly motivated. We have projected the need to recruit 60 subjects to reach 40 complete studies, for a potential dropout rate of 33%. To improve retention, the PIs will interact individually with the patients, and we will make maximal use of one-on-one instruction and education, and frequent contact with participants, in addition to small financial incentives. In the past, our drop out rate has been about 10%, once the subject passes the initial screening procedures. This is low, but it reflects the fact that we are experienced at recruiting and motivating subjects. In addition, subjects must be willing to go through a number of initial procedures, so casual study subjects do not usually enroll.

b. Sources of Materials

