Adipose tissue, and blood samples will be obtained from subjects, and these tissues will be used exclusively for research purposes. From a blood sample, DNA will be prepared. Under no circumstances will the patients' clinical care be compromised.

c. Potential Risks

Risks of the biopsies include bleeding, infection, and pain and patients are told of this. [name] is very experienced in this procedure and has an excellent track record. Rarely (<1%) have oral antibiotics been needed following a biopsy.

The lipid tolerance test involves the consumption of a liquid meal containing corn oil and cream, followed by hourly blood draws. Some subjects may have mild GI symptoms, but this will likely be minimal. Of the subjects studied to date, none have had GI symptoms, and all consumed their beverage within 10 min.

The clamp involves frequent blood draws and indwelling catheters. There is some needlestick discomfort, and there is a risk of hypoglycemia, although blood glucose is monitored carefully.

Antibiotic treatment with rifaximin. In clinical studies of rifaximin, the side effects are very low, usually similar to that of the placebo treated group. In studies involving the use of rifaximin for travelers diarrhea, the only side effect of rifaximin that was higher than placebo was flatulence (20% vs 11% in placebo) (Xifaxan® package insert: http://www.salix.com/assets/pdf/prescribe_info/xifaxanpi.pdf). In the package insert, post-marketing experience states that *C. difficile* associated diarrhea has been reported in patients taking rifaximin, and the "Warnings and precautions" statement states that "*C. difficile* diarrhea has been reported with rifaximin as it has been reported with all other antibiotics". Notwithstanding these isolated reports of *C. difficile*, this complication has not been a problem with the use of rifaximin in clinical trials. For example, in the TARGET study, 625 subjects with IBS were randomized to rifaximin, and there were no cases of *C. difficile* (67). Indeed rifaximin is used to treat *C. difficile* diarrhea, including metronidazole-resistant *C. difficile*, and to prevent recurrence (78;79).

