The attribution scale for AE reporting will be as follows. Probable: AE is related to the procedure (e.g. infection from a fat biopsy). Possible: AE follows the procedure within a reasonable period (within 7 days), but may have been produced by the subject's clinical state or other factors (e.g. rash 3 days following the clamp). Remote: AE does not follow the procedure or drug within a reasonable period and could readily have been produced by the subject's clinical state or other factors. Unrelated: AE is judged to be clearly due to extraneous causes and does not meet the above criteria.

Plan for unexpected Adverse event (AE) reporting. Serious AEs will be reported to Human Subjects/IRB within 48 hr, and will also be reported to the CR-DOC. Unanticipated events will be reported to the CR-DOC real time, and to the IRB no later than 15 days after the event. Annual reporting of adverse events will be conducted with the Human Subjects annual review/renewal according to their guidelines.

Monitoring of adverse events. Adverse events will be monitored via exams, vital signs, lab tests, review of subject's medical chart, review of subject diaries, etc. and documented. Signs of infection from the biopsies will be monitored by exams. Each visit will be documented with a progress note in the CR-DOC chart. A data safety and monitoring board (DSMB) will oversee the safety of this project. The University of Kentucky CTSA has a Research Participant Advocate who chairs a DSMB, and this DSMB will perform a periodic review of this protocol. No provision is made to compensate patients for any research related injury, and this is stated in the consent form.

Inclusion of Women and Minorities

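### The adverse-event attribution scale ties Probable and Possible to procedures only, so an event caused by the study drug has no category that says so

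*Combined protocol and SAP*

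**What the plan says.** The Data & Safety Monitoring Plan sets out one attribution scale for adverse events, with four levels:

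- "Probable: AE is related to the procedure (e.g. infection from a fat biopsy"). No time limit is attached.
- "Possible: AE follows the procedure within a reasonable period (within 7 days"), with the allowance that the subject's condition or something else may have been the cause. The example is "e.g. rash 3 days following the clamp".
- "Remote: AE does not follow the procedure or drug within a reasonable period", together with the statement that other factors could readily explain the event.
- "Unrelated: AE is judged to be clearly due to extraneous causes and does not meet the above criteria".

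On exposure, Specific Aim 1 states: "Subjects will then begin taking rifaximin 550 mg BID or placebo for 8 weeks". The Intervention paragraph under Protection of Human Subjects gives the order: "After the above procedures, subjects will then begin taking rifaximin". All procedures are then repeated after 8 weeks of treatment. The only assessment scheduled at week 4 is a diet record (Recruitment of study subjects).

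On drug risks, the Potential Risks section reports flatulence in 20% on rifaximin against 11% on placebo in travelers' diarrhea studies. It also cites the package insert, according to which *C. difficile* associated "diarrhea has been reported in patients taking rifaximin". The protocol undertakes to educate subjects about these symptoms and to monitor for them.

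No other section, including the Statistical Analysis Plan, gives a rule for attributing an event to the drug.

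**The concern.** This is a drug-versus-placebo trial, and the protocol itself names the drug effects it expects or wants to watch. A relatedness scale should let the rater say that such an event may be, or probably is, due to the drug. Here both levels that express a link are worded for procedures, and both of their examples are procedural (a biopsy infection, a rash after the clamp). The drug enters only in the level that denies a timely link.

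At stake is the meaning of the relatedness rating for drug events. If the scale is followed as written, a rater facing an on-treatment gastrointestinal event must leave it unclassified, choose a level whose definition is not met, or read into the text something it does not say. Different raters may choose differently, and some of these choices would understate a link to the drug.

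**Working it through.** No sample size, power or event count bears on this point. The check is a literal reading of the four definitions against events that could occur under the protocol's schedule.

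**Does procedure include the drug?** Remote lists the procedure and the drug as alternatives. If the first term already covered the second, the second would be redundant. So procedure in Probable and Possible cannot safely be read to include the drug.

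**When do procedures occur?** Baseline procedures come before dosing, and the repeat procedures come after 8 weeks of treatment (8 × 7 = 56 days). No procedure is scheduled between. The interval between the last baseline procedure and the first dose is not given.

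**Two test events, both assumed to be caused by the drug:**

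| Level | Diarrhea in week 5 of dosing | Flatulence on an early dosing day, within 7 days of a baseline procedure |
|---|---|---|
| Probable | Not met: no relation to a procedure | Not met: no relation to a procedure |
| Possible | Not met: no procedure in the previous 7 days | Met on timing, but only as an event following the procedure |
| Remote | Not met: the event does follow the drug | Not met: the event follows both |
| Unrelated | Not met: the cause is not extraneous | Not met: the cause is not extraneous, and Possible is met |

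Two separate results follow.

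1. *Every dosing day.* No level records a link to the drug. In the second column a label is available, but it attributes the event to the wrong exposure.
2. *On-treatment days more than 7 days after a procedure.* A drug-caused event meets none of the four definitions. This is a gap in the scale and not a default to Remote, because Remote requires that the event does not follow the drug in reasonable time.

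The 7-day limit belongs to Possible alone. Probable has no time limit and is closed to drug events by its wording. A late procedural event, such as a biopsy infection appearing after 7 days, can still be rated Probable.

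**The case against.** The strongest reply is that the omission is a slip that does little harm. Remote tests for a link to the procedure or the drug, which shows that the scale was meant to cover both. An investigator would probably supply the missing words. This is a fair account of the intent, and it makes the problem an internal inconsistency rather than a deliberate choice. It does not remove the problem: a written scale exists so that raters need not guess, and nothing elsewhere fills the gap.

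The second reply stands in full: the main safety steps do not depend on attribution. Serious events go to the IRB within 48 hours. Unanticipated events go to the CR-DOC in real time and to the IRB within 15 days. Adverse events are sought through exams, laboratory tests, chart review and diaries, and are documented. A DSMB reviews the protocol periodically. For *C. difficile*, subjects are given symptoms that should prompt an immediate call, and gastroenterologists are involved. Neither detection nor expedited reporting is lost.

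Two stronger readings are tempting, and the documents support neither.

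- A reader might infer that the DSMB and IRB will see attribution tables that understate drug-related events. No such tables are described; the text provides only for periodic DSMB review and annual reporting under IRB guidelines. Understatement is possible, not established.
- A reader might take the first 7 of the 56 dosing days as covered and conclude that 49/56 = 87.5% of exposure is affected. That assumes the last baseline procedure falls on the day of the first dose, which the documents do not say. It also measures the wrong thing: the window belongs only to Possible, and drug attribution is missing inside the window as well as outside it.

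**Conclusion.** The inconsistency is real and should be corrected. As written, the scale offers no level for drug-relatedness on any dosing day, and a drug-caused event on treatment more than 7 days after a procedure fits no level at all.

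The consequence is limited to the relatedness label, and falls mainly on non-serious, expected drug events such as flatulence or diarrhea. How many events would be affected cannot be derived from the documents, and no percentage is claimed.

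The conclusion rests on a literal reading of the four definitions and on the schedule showing no procedure during the 8 weeks of dosing. If investigators in practice read the drug into Probable and Possible, the effect shrinks to inconsistency between raters.

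**What to change.** In the Data & Safety Monitoring Plan, reconcile the four definitions:

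- **Probable:** extend it to an event related to the procedure or to the study drug.
- **Possible:** extend it to an event that follows the procedure or the study drug within a reasonable period. Keep the existing allowance that the subject's condition or other factors may be responsible. Without it, and with a definition as loose as any event while on drug, nearly every on-treatment event in both arms would be rated Possible and the label would no longer discriminate.
- **Time period for the drug:** the study physicians should state what counts as reasonable and use the same meaning in Remote. No length is proposed here.
- **Recording:** enter attribution to procedure and attribution to study drug in separate fields, so that an event soon after a procedure while on drug can be rated against each.

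The cost is two revised definitions, with Remote aligned to them, and one extra field on the adverse-event form. Visits, assessments and sample size are unaffected. If events have already been rated, those that occurred on treatment should be rated again under the revised wording.

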An important outcome will be the measurement of LPS in plasma and lipoprotein fractions from the low-fat and the high-fat meals, and we will examine the peak LPS levels, as well as area under the curve. In a previous study in lean subjects, baseline LPS was 0.39 ± 0.07 EU/ml and increased to 0.58 EU/ml with a fatty meal (53). Assuming that SD of the group and SD of change is 0.1 and an effect size of 1.0, we will need 10 subjects to detect a change of 0.1 EU/ml between a low-fat and high fat meal (paired T-test) and 17 subjects to detect the same difference between groups (drug vs placebo), with α of 0.05 and 80% power. Our preliminary data support the effect size described. To estimate the sample size needed to observe changes in adipose tissue inflammation, we will target adipose tissue macrophages. In previous studies of obese/IR subjects, macrophage number was $34 \pm 5.8/\text{mm}^2$ (31). Assuming the SD of change is equal to the SD 5.8 in these obese subjects, 20 subjects in each group will allow us to detect a change in macrophage number of $4/\text{mm}^2$ with 80% power using a paired t-test. For comparisons between groups, if we assume an effect size of 1.0, we will need to recruit 17 subjects in each group. In previous interventional studies, we detected changes in macrophage number in adipose in response to fish oil and pioglitazone treatment (35;77). These sample size calculations project adequate power with a total of 40 subjects (20 in each group) who complete the whole protocol. We recognize that we are asking a lot of these subjects, however we have considerable experience performing similar in-depth studies. We anticipate a higher drop-out rate than usual, and we estimate that we will need to recruit 60 subjects to obtain 40 that complete the protocol.

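### The two meals are given on separate days in randomised order, but the only test named for comparing them, a paired t-test, has no order or test-day term

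*Combined protocol and SAP*

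**What the plan says.** The protocol, under Specific Aim 1, sets the design of the meal comparison: "All subjects will undergo a fat tolerance test on two different days, in random order, with two different amounts of lipid in the meal". After treatment, "all subjects will repeat the lipid tolerance tests (low- and high fat". The Intervention paragraph under Protection of Human Subjects also says that both tests are repeated.

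The section headed Statistical Analysis Plan repeats the protocol's Sample size paragraph and adds nothing. For the meal contrast it says "we will need 10 subjects to detect a change of 0.1 EU/ml between a low-fat and high fat meal (paired T-test", under the assumption "Assuming that SD of the group and SD of change is 0.1 and an effect size of 1.0". For the arms it gives "17 subjects to detect the same difference between groups (drug vs placebo", in both cases "with α of 0.05 and 80% power". The outcomes are peak LPS and area under the curve, and 40 completers are planned, 20 per group.

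The documents do not state an analysis model for the meal contrast, a term for meal order, test day or carryover, whether the two orders are balanced, the interval between test days, or whether the week-8 order follows the baseline order.

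**The concern.** Two conditions per subject on two days in randomised order make a two-period crossover. A plain paired t-test uses the within-subject difference but discards the order. Suppose LPS differs systematically between first and second test day. Each high-minus-low difference is then raised by that shift in subjects who take the low-fat meal first, and lowered by it in the others. Without an order term this known pattern is treated as noise, and an unequal split of orders leaves part of it in the mean.

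Whether more dietary fat raises LPS is an explicit question of Aim 1, so an interval wider than necessary has a cost. The same shift can also reach the central comparison, rifaximin against placebo. If a subject takes a given meal first at baseline and second at week 8, the day shift enters that meal's change score.

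**Working it through.** **Inputs from the Sample size text and the SAP.** Difference 0.1 EU/ml; SD of the group and SD of change 0.1; alpha 0.05; power 80%; n = 10 for the meals and 17 for drug versus placebo; 40 completers. Sidedness is not stated; two-sided reproduces the figures. **Assumed:** a first-to-second-day shift D of 0.05 to 0.10 EU/ml, because the documents give none.

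**1. The plan's figures.** Paired t-test, noncentral t, effect size 0.1/0.1 = 1.0: n = 9 gives 74.8% and n = 10 gives 80.3%. Two-sample t-test, effect size 1.0: 16 per group gives 78.1% and 17 per group gives 80.7%. Both stated sizes reproduce, reading 17 as per group.

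**2. Meal contrast without an order term, orders balanced.** The difference has mean (meal effect + D) in one order and (meal effect - D) in the other, so its SD is about √(0.1² + D²).

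| D (EU/ml) | SD of difference | Effective n of 40 = 40 × 0.1²/SD² | 95% half-width, 2.023 × SD/√40 | Power, n = 10 | Power, n = 40 |
|---|---|---|---|---|---|
| 0 | 0.100 | 40 | 0.032 | 80% | >99% |
| 0.05 | 0.112 | 32 | 0.036 | 71% | >99% |
| 0.10 | 0.141 | 20 | 0.045 | 51% | >99% |

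Simulation with an exact 5/5 split gives 72% and 48% in place of 71% and 51%.

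**3. Unequal orders.** For a split n1/n2 the estimate moves by D(n1 - n2)/n.
- 23/17: 6/40 = 15% of D, that is 0.0075 to 0.015 EU/ml. If order is allocated without restriction, a split at least this uneven has probability 0.43 (Binomial(40, 0.5)). Type I error at 23/17 stays at or below 5%.
- 26/14: 12/40 = 30% of D, that is 0.015 to 0.030 EU/ml. A split at least this uneven has probability about 0.08. Type I error, given that split, is 10.8% for D = 0.05 and 19.3% for D = 0.10.
- Averaged over simple randomisation of order, the bias is about zero and the type I error is 5.0% to 5.3% at n = 10 and 5.0% at n = 40.

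**4. With the order term.** The estimate is the average of the two order-specific means, with SE = (0.1/2)√(1/n1 + 1/n2) and n - 2 degrees of freedom. At 20/20 the SE is 0.0158 and the half-width 0.032, whatever D is. Power at n = 10 (5/5) is 79.1%, against 80.3% for the paired t-test when D = 0.

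**5. Drug versus placebo, one meal, week-8 order independent of baseline.** The day shift in the change score is -D, 0 or +D with probabilities 1/4, 1/2 and 1/4, so its variance is D²/2 and the SD of change is √(0.1² + D²/2).

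| D (EU/ml) | SD of change | Power, 17 per group | Power, 20 per group |
|---|---|---|---|
| 0 | 0.100 | 81% | 87% |
| 0.05 | 0.106 | 76% | 83% |
| 0.10 | 0.122 | 64% | 71% |

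**6. If the SD of 0.1 already contains the shift.** The residual SD is then smaller than 0.1, and the order term raises power at n = 10 to 82% (D = 0.025) or 90% (D = 0.05).

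**The case against.** The strongest reply is that the plan never prescribes a paired t-test as the analysis. The test appears in parentheses as the basis for n = 10, and that figure is right. This stands: a reader might infer that the SAP specifies a wrong test, but what it lacks is any model at all. The paired t-test remains the only method a reader can attach to the meal contrast.

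Second, randomised order protects the simple test. This also stands. A reader might infer that the meal effect will be biased, but over the randomisation it is not, and the test keeps about its 5% level. The displacement depends on the split obtained; at 23/17 it is at most 0.015 EU/ml, below one standard error at 40 subjects (0.1/√40 = 0.0158).

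Third, no shift is documented. The evening meal, the 12-hour fast and abstinence from alcohol before each test are standardised. The upper assumed value of 0.10 equals the whole target difference and is over half of the fatty-meal rise the plan cites (0.58 - 0.39 = 0.19). The plan's SD may already include a shift. All of this is fair and makes the losses conditional. It does not count against the adjustment, which costs almost nothing when D is zero and gains precision when the SD includes the shift.

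Fourth, only a systematic shift common to subjects can be removed. Ordinary within-subject variation from day to day stays in the error under either analysis.

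Fifth, the drug-contrast loss needs both a day shift and a week-8 order unrelated to baseline. The protocol says only that the tests are repeated. At D = 0.05, power at 20 per group remains above 80%.

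**Conclusion.** The point holds as a low-cost improvement. The trial randomises meal order, and nothing in the documents uses that order in the analysis or controls its balance. For an assumed D of 0.05 to 0.10 EU/ml, added to an SD of 0.1, the result is lost precision in the meal contrast: a half-width of 0.036 to 0.045 in place of 0.032.

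A reader might infer that n = 10 is too small or that the meal comparison is underpowered. The documents support neither: n = 10 follows from its own inputs, and it is understated only if the SD of 0.1 excludes a real shift. The drug-versus-placebo loss is the more consequential possibility, because that comparison has less power to spare, but it rests on two things the text leaves open.

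**What to change.** In the SAP, state the analysis of the meal contrast for peak LPS and AUC as a model with meal, test day and subject. At a single visit, regressing the within-subject difference on meal order is equivalent for subjects with both tests. Balance the meal order in blocks within each arm, and give each subject the meals in the same order at week 8 as at baseline.

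The cost is one degree of freedom (about 79% against 80% power at n = 10 when there is no shift, negligible at 40) and one scheduling rule. No visits, samples or subjects are added. The test-day term does not remove carryover that differs by meal, so the SAP should not claim that it does.

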Recruitment of study subjects. We intend to recruit 40 non-diabetic subjects (sample size below) with obesity (BMI 30-40), ages 45-60, and evidence of MetS or IR. Each subject will undergo a fat tolerance test with both a low fat and high fat meal. We wish to avoid very obese subjects (BMI > 40) because of the large amount of lipid that will be consumed (see below). All subjects will initially have a standard 75g OGTT with measurement of glucose and insulin to characterize glucose tolerance and to obtain measures of insulin sensitivity and secretion using the Matsuda index (64;65). We will include subjects with IGT, IFG, as well as NGT subjects if they have at least 3 features of MetS (Table 1). Based on our considerable experience, essentially all of these obese subjects will be IR when the euglycemic clamp is performed. Exclusion criteria will include GI conditions (IBS, lactose intolerance) and the use of lipid lowering or antiinflammatory drugs. These subjects will have the following procedures performed at baseline and after drug/placebo treatment: OGTT, lipid tolerance tests, body composition (DEX), plasma inflammatory markers, adipose biopsy, insulin sensitivity, and gut microbiota assessment, as described below. Diet information will be recorded using a web-based software (9) at baseline, 4 and 8 weeks, and subjects will be asked to stay on their usual diet.

Table 1. Inclusion criteria	
Males & females, all ethnic groups, A1C<6.5	
BMI	30-40
Age	45-60
OGTT; features of MetS*	IGT, IFG, or NGT +3
*IGT: FBS< 126 mg/dl, 2 hr: 140-199; IFG: FBS 101-125, 2 hr ≤199; MetS: TG>150 mg/dl, HDL<40 (M) or <50 (F), BP>130/85 or on treatment, Waist >40" (M) or >35" (F) ; NGT: normal glu tolerance	

Specific Aim 1. We will determine whether an alteration in the gut microbiota achieved with rifaximin will decrease circulating LPS. We will recruit obese human subjects with MetS or impaired glucose tolerance. An oral fat tolerance test will be performed at two different fat doses with measurement of plasma chylomicron-associated LPS and LBP, and measurement of LPS and LBP in the other lipoprotein fractions (using Westerns for LBP). Subjects will then be treated with the antibiotic rifaximin for 8 weeks to alter the gut microbiota. The lipid tolerance tests will be repeated to determine whether the antibiotic treatment reduces post-prandial LPS and alters the distribution of LPS in lipoproteins.

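### The SAP names no test for drug versus placebo and no baseline adjustment; a model adjusted for baseline should be specified for each comparison

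*Combined protocol and SAP*

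**What the plan says.** The Statistical Analysis Plan repeats the protocol's Sample size paragraph, and no other section describes statistical methods. For LPS it starts from "Assuming that SD of the group and SD of change is 0.1 and an effect size of 1.0". It gives 10 subjects to "detect a change of 0.1 EU/ml between a low-fat and high fat meal (paired T-test") and then "17 subjects to detect the same difference between groups (drug vs placebo"), "with α of 0.05 and 80% power". For adipose macrophages it uses a paired t-test for a within-group change of 4/mm², with the premise "Assuming the SD of change is equal to the SD 5.8 in these obese subjects", and then adds: "For comparisons between groups, if we assume an effect size of 1.0, we will need to recruit 17 subjects in each group". The target is "a total of 40 subjects (20 in each group) who complete the whole protocol".

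The paired t-test is the only test named. For drug versus placebo there is an effect size and a number, but no test, no choice between post-treatment values and changes, and no covariate.

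Under Recruitment of study subjects the protocol says: "These subjects will have the following procedures performed at baseline and after drug/placebo treatment". The list that follows covers the lipid tolerance tests, biopsy, insulin sensitivity and plasma markers. Anticipated Outcomes likewise lists LPS, insulin sensitivity, plasma and adipose markers and macrophage measures as examined before and after rifaximin or placebo.

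**The concern.** With the between-group analysis unnamed, three analyses remain open after the data are seen: a t-test on post-treatment values, a t-test on changes, and a baseline-adjusted model. They can give different answers. With 20 per arm, the standard error of a chance difference in baseline means is √(2/20) = 0.32 SD, so visible imbalance is likely. A post-treatment comparison carries that imbalance into the estimate, and a change score over-corrects it whenever the baseline slope is below 1. Adjusting for baseline removes it and usually narrows the confidence interval, using measurements the protocol already collects. Completers are scarce here: each undergoes repeated clamps, biopsies and fat tolerance tests, and one third are expected to drop out.

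**Working it through.** **Inputs from the SAP.** α 0.05 and 80% power (sidedness not stated); LPS SD of group and of change both 0.1 EU/ml; macrophage SD and SD of change both 5.8/mm²; between-group effect size 1.0; 20 completers per group. **Assumption.** The baseline to post-treatment correlation r is not stated, so it is varied from 0 to 0.7.

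**1. The plan's own figure.** Two-sample t-test, noncentral t, d = 1.0, two-sided α 0.05, noncentrality d√(n/2), df = 2n − 2:
- n = 16 per group: 78.1%
- n = 17 per group: 80.7%
- n = 20 per group: 86.9%

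So 17 per group is reproduced. A one-sided t-test would need only 14, so the calculation is two-sided. The paired figures also hold: n = 10 gives 80.3% at d = 1.0, and n = 20 gives 83.3% for 4/mm² with SD 5.8.

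**2. What the SD assumption implies.** With equal SDs before and after treatment, SD²(change) = 2·SD²·(1 − r). Setting SD(change) = SD gives r = 0.5. The macrophage sentence is about change on treatment, so 0.5 is the plan's own implication there. The LPS sentence goes on to the low-fat versus high-fat contrast, so its change may be between meals, and r = 0.5 for baseline to week 8 is then an assumption. At r = 0.5 a t-test on post-treatment values and one on changes have the same SD, so the figure of 17 cannot show which was meant.

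**3. Adjusting for baseline.** ANCOVA residual SD = SD·√(1 − r²), with df = 2n − 3. At r = 0.5 this is √0.75 = 0.866 SD, a 25% cut in variance. The lower end of each ANCOVA range below also multiplies the variance by 1 + 1/(2n − 4), the average precision lost to chance baseline imbalance (1 + 1/36 at n = 20).

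Power at 20 per arm for a difference of 1.0 SD:

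| r | Post-treatment t-test | Change-score t-test | ANCOVA |
|---|---|---|---|
| 0 | 86.9% | 58.7% | 85.9-86.8% |
| 0.3 | 86.9% | 74.0% | 89.0-89.8% |
| 0.5 | 86.9% | 86.9% | 93.9-94.5% |
| 0.7 | 86.9% | 97.8% | 98.9-99.1% |

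The table holds the group SD fixed and lets the SD of change follow r. At r = 0.3 the SD of change is 0.1·√1.4 = 0.118, so rows other than r = 0.5 depart from the plan's premise that both are 0.1. A simulation of 10,000 trials at r = 0.5 and 20 per arm gave 86.6% (post-treatment), 87.1% (change) and 93.8% (ANCOVA).

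**4. Numbers needed and detectable differences at r = 0.5.** For 80% power at d = 1.0, ANCOVA needs 13 per arm without the imbalance allowance (80.5%) and 14 with it (13 gives 78.7%, 14 gives 82.0%), against 17 unadjusted. At 20 per arm the difference detectable with 80% power falls from 0.91 SD to 0.79-0.80 SD. For macrophages that is 0.91 × 5.8 = 5.3/mm² down to 0.79-0.80 × 5.8 = 4.6/mm².

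**The case against.** The strongest reply is that the plan is adequate as sized. The 17 per group reproduces, 20 completers exceed it, and no between-group power target in the plan is missed. Powering on an unadjusted effect size is conservative and compatible with a later adjusted analysis. This stands: the point concerns an unspecified analysis and an available gain in efficiency, not a wrong sample size.

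Four stronger readings are tempting, and the documents do not support them.

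- *A reader might infer that the SAP plans unadjusted t-tests for drug versus placebo.* It does not say so. The wording is a sample-size statement, and a change-score test, which already uses baseline, fits the same number.
- *A reader might take r = 0.5 as the plan's own figure for LPS.* That holds only if change there means before to after treatment.
- *A reader might note that a 4/mm² between-group macrophage difference has only 57% power unadjusted (4/5.8 = 0.69 SD, 20 per arm), rising to 68-69% with ANCOVA, and call this a shortfall.* The plan sets 4/mm² for the within-group paired test. Its between-group target is 1.0 SD, or 5.8/mm², where unadjusted power is already 87%.
- *A reader might call the adjustment free.* It costs one degree of freedom and some precision; at r = 0, power at 20 per arm falls from 86.9% to as low as 85.9%.

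One further limit stands. The argument from chance imbalance presumes random assignment to arm, which the documents do not describe. The random order in Specific Aim 1 concerns the two meals.

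**Conclusion.** The point holds as a gap in specification with a better method at hand. The SAP leaves the drug-versus-placebo analysis unnamed and mentions no baseline adjustment, although baseline values are collected. At effect size 1.0 and 20 per arm, ANCOVA changes power from 87% to somewhere between about 86% and 99% over r from 0 to 0.7, and to about 94% at r = 0.5. It is also the safer choice while r is unknown: it stays within about one point of the post-treatment test at worst and is above the change-score test at every value of r tabulated. The sizes rest on normal outcomes, equal SDs before and after treatment, a common slope in both arms, random assignment, and an r that is implied for macrophages but assumed for LPS.

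**What to change.** Add to the SAP: each drug-versus-placebo comparison is a linear model of the post-treatment value on arm and the baseline value of the same measure (from the same meal for LPS peak and area under the curve), reporting the adjusted difference with its 95% confidence interval. Keep the stated within-group paired t-tests, including the one for macrophages, as supportive analyses, and keep the paired test for the meal contrast. State how subjects are assigned to drug or placebo, because the adjusted comparison relies on that assignment being random.

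Leave the target of 20 completers per group unchanged. The cost is SAP wording, one degree of freedom per model, and up to about one point of power if r is near zero. No extra visits, samples or subjects are needed.
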